Pharmacokinetic sampling ⁽ⁿ⁾	X (Cycle 3, Infusions 1, 5)	X (Cycle 3, Infusions 1, 5)						
Immunogenicity sampling ^(o)	X (Infusion 1)			X				
Vision assessment					X	X		
AE and SAE monitoring	X	X	X	X	X		X	
Long-term follow-up ^(p)							X	X

- (a) Vital signs should be performed after patient is sitting for 3-5 minutes. If during dosing period, vital signs should be taken immediately prior to infusion, immediately after completion of infusion, and 30, 60, and 240 minutes post-infusion.
- (b) All patients will have a 12-lead ECG performed at the screening visit and pre-treatment visit, as well as Day 21 (and Day 28 only if delayed end of cycle) of each cycle. During the days when patients are undergoing PK sampling (Cycle 1, infusions 1 and 5; Cycle 3, infusions 1 and 5), an ECG will be performed at 3 distinct time points (triplicates) within 5 minutes prior to each PK sample collection pre-infusion and at 30 and 60 minutes post-infusion (see (m) and [Table 9](#)).
- (c) To be collected prior to SL-401 infusion if during dosing period. Hematology includes White blood cell (WBC) count, differential white cell count, red blood cell count, hematocrit, hemoglobin and platelet count.
- (d) To be collected prior to SL-401 infusion if during dosing period. Electrolytes include sodium, potassium, bicarbonate, chloride, blood urea nitrogen (BUN), and creatinine.
- (e) To be collected prior to SL-401 infusion if during dosing period. Serum albumin may be a component of the chemistry panel (f). See protocol for administration of albumin if serum albumin decreases during treatment days or in the immediate post-treatment period.
- (f) To be collected prior to SL-401 infusion if during dosing period. Serum electrolytes and chemistry: Sodium, potassium, bicarbonate, chloride, blood urea nitrogen (BUN), creatinine, glucose, alanine aminotransferase (ALT), albumin, alkaline phosphatase (ALP), aspartate aminotransferase, (AST), bilirubin (total, direct, and indirect), calcium, creatine phosphokinase (CPK), magnesium, lactate dehydrogenase (LDH), phosphate, total protein, uric acid
- (g) To be collected prior to initial SL-401 infusion of the cycle. Urinalysis includes appearance, color, pH, specific gravity, ketones, leukocytes, protein, glucose, bilirubin, urobilinogen, and occult blood.
- (h) Morphology and differential WBC/blast count on aspirate. In Stages 2-4, patients with evidence of bone marrow involvement prior to study will have bone marrow evaluations following Cycles 4 and 6 and then every 3 months from Months 6-12; every 6 months from 12 to 24 months; and every 12 months thereafter until there is evidence of relapsed or progressive disease. If CD123 flow cytometry stain was performed on the bone marrow aspirations (\pm biopsy), the results should be recorded in the eCRF.
- (i) Baseline CT must be performed within 14 days prior to the first administration of SL-401. For patients with baseline evidence of lymph node or visceral disease involvement, subsequent Stages 2-4 CT scans will be performed 21 (\pm 7) days after the start of Cycles 1, 2, 4 and 6, and 21 (\pm 7) days after the start of every 4th cycle thereafter (approximately every 12 weeks) until there is evidence of relapsed or progressive disease. For patients with no baseline evidence of lymph node or visceral BPDNCN involvement, subsequent scans should be performed at the end of Cycle 2 (\pm 7 days; or at time of disease progression if PD occurs prior to end of Cycle 2), 21 (\pm 7) days after the start of Cycle 6, and at Investigator's discretion thereafter. Baseline CT scans should be full-body, whereas follow-up scans should document response of index lesions.
- (j) For patients with skin involvement. Baseline must be performed within 14 days prior to the first administration of SI-401. Subsequent skin assessments will be performed 21 (\pm 7) days after the start of Cycles 1 and 2 and 21 (\pm 7) days after the start of every 2nd cycle thereafter (Cycles 4, 6, etc.) until there is evidence of relapsed or progressive disease. Quantification of skin disease burden via the mSWAT instrument is required at the time of each skin assessment.
- (k) Peripheral blood samples will be collected 21 (\pm 7) days after the start of Cycles 1 and 2 and, for patients with evidence of peripheral blasts at baseline, 21 (\pm 7) days after the start of every 2nd cycle thereafter (Cycles 4, 6, etc.) until there is evidence of relapsed or progressive disease.
- (l) Refer to protocol [Section 7.5.3.1](#) – Premedication and Administration
- (m) Following treatment with premedication, SL-401 will be administered as a 15-minute infusion for the first 5 consecutive days of a 21-day cycle. Individual SL-401 infusions may be delayed to allow for toxicity resolution; all infusions should be completed within 10 days and fewer than 5 infusions are permitted in settings of incipient CLS or hepatotoxicity. Patient must be monitored for 4 hours post infusion.
- (n) Plasma samples (6 mL each) will be collected immediately prior to the start of the infusion of SL-401, immediately after end of infusion (time recorded), then 15, 30, 45, 60, 90, 120, 180, and 240 minutes after the start of the infusion during infusions 1 (i.e., Day 1) and 5 (i.e., Day 5) of [Cycles 1 & 3](#) (see [Table 9](#)).
- (o) Blood samples (10 mL) will be collected for the detection of SL-401 reactive antibodies on Day 1 (pre-infusion), Day 15, and Day 21 (if patient is to receive additional cycles, can be Day 1, pre-infusion for next cycle). If infusions are held, please collect a sample within 3 \pm 3 days after the last SL-401 infusion of the cycle.
- (p) After the follow-up visit, patients will then be followed every 90 days for survival status. The survival follow-up may be by telephone contact. If the patient is in CR/PR at the time of discontinuation, disease assessments should continue to be performed as described in [Section 8.12](#) on an every 6-week basis (\pm 1 week) through 6 months post-C1D1 and then on an every 90-day basis or until, in the judgment of the Investigator, there is evidence of relapsed or progressive disease. Patients who undergo SCT will be followed for the occurrence of VOD and delayed or failed engraftment as part of survival monitoring.
- (q) For Cycles 5 and beyond (Stages 2-4), the Day 8 and 15 concomitant medication and AE evaluations may be conducted via telephone and the laboratory evaluations may be performed at local laboratories for patients who live a considerable distance from the study center.

Table 9: Time Points for Pharmacokinetic Blood Draws and ECGs

Time Point	Cycle: Day/Dose							
	Cycle 1: Day 1/Infusion 1		Cycle 1: Day 5/Infusion 5		Cycle 3: Day 1/Infusion 1		Cycle 3: Day 5/Infusion 5	
	ECG	PK	ECG	PK	ECG	PK	ECG	PK
Pre-Infusion	X	X	X	X	X	X	X	X
Immediately After End of Infusion (time recorded)		X		X		X		X
15 Minutes Post-Infusion		X		X		X		X
30 Minutes Post-Infusion	X	X	X	X	X	X	X	X
45 Minutes Post-Infusion		X		X		X		X
60 Minutes Post-Infusion	X	X	X	X	X	X	X	X
90 Minutes Post-Infusion		X		X		X		X
120 Minutes Post-Infusion		X		X		X		X
180 Minutes Post-Infusion		X		X		X		X
240 Minutes Post-Infusion		X		X		X		X

ECGs will be performed at 3 distinct time points (triplicates) within 5 minutes prior to each PK sample collection at the time points indicated.

10 Adverse Events and Safety Evaluation

The AE reporting period for a patient treated in the study begins with the initiation of SL-401 and is continuous through 30 days after the last SL-401 infusion. All AEs that occur in treated patients during the AE reporting period specified in the protocol must be reported to the Sponsor or designee, whether or not the event is considered related to SL-401. Any known untoward event that occurs beyond the AE reporting period that the Investigator assesses as related to SL-401 should also be reported as an AE.

All patients should be monitored per institutional guidelines for at least 4 hours following the administration of each infusion of SL-401. The Principal Investigator, who is a physician, or medical staff responsible for study conduct and safety evaluations, should be available during the administration SL-401 and follow-up to assess, treat, or report as necessary any AE or serious adverse event (SAE) that may occur.

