7.5.4 Patient Monitoring Procedures During the SL-401 Dosing Period

To assess relevant acute toxicities, testing and procedures summarized below are to be performed and results are to be reviewed prior to each scheduled SL-401 infusion (refer to [Section 9.8](#) [Table 5](#), [Table 6](#), [Table 7](#), and [Table 8](#) for more detail):

- Vital signs including blood pressure, heart rate, respiration rate, body temperature, and pulse oximetry:
 - During daily dosing (usually Days 1, 2, 3, 4 and 5):
 - immediately prior to infusion,
 - immediately after completion of infusion, and
 - 30, 60, and 240 minutes post-infusion.
 - Days 8, 15, and 21.
- Diagnostic blood tests during daily dosing (usually Days 1, 2, 3, 4 and 5) and Days 8, 15, and 21 as follows:
 - Hematology: complete blood count (CBC) with differential, platelet count;
 - Serum Electrolytes and Chemistry: sodium, potassium, bicarbonate, chloride, blood urea nitrogen (BUN), creatinine, glucose, alanine aminotransferase (ALT), albumin, alkaline phosphatase (ALP), aspartate aminotransferase, (AST), bilirubin (total, direct, and indirect), calcium, creatine phosphokinase (CPK), magnesium, lactate dehydrogenase (LDH), phosphate, total protein, uric acid;
 - Coagulation: prothrombin time (PT) or International Normalized Ratio (INR), and activated partial thrombin time (aPTT).
- Routine urinalysis on Day 1 (prior to SL-401 infusion), and Days 8, 15, and 21.

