9.3.5 Study Day 21 \pm 7 Days: End of Cycle

Note: The end-of-cycle evaluations (Day 21 or thereafter) may also serve as the pre-infusion evaluations for the subsequent cycles; with the exception of vital signs, these do not need to be duplicated on successive days unless there is an abnormality or other clinically relevant reason for repeat evaluation.

All Patients, All Study Stages:

- Concomitant medication assessment
- ECOG performance status
- Physical examination
- Vital signs and weight
- 12-lead ECG
- Clinical laboratory tests: hematology, serum electrolytes and chemistry (including albumin), coagulation parameters, and urinalysis
- Tumor response assessment: bone marrow aspiration (\pm biopsy) and peripheral blood sample (AML and BPDCN). If the Cycle 1 (Day 21 [\pm 7]) bone marrow examination is empty (i.e., hypocellular) or inadequate, a bone marrow examination should be repeated in 7 (\pm 7) days to document response. If additional time is required to complete the repeat examination, consult with the Medical Monitor. If CD123 flow cytometry or IHC stain was performed on the bone marrow aspirations (\pm biopsy), then the results should be recorded in the eCRF.

- Collection of peripheral blood (serum) for immunogenicity
- Monitoring for changes in visual acuity and color vision
- AE and SAE monitoring

Patients with BPDCN Only:

- Tumor response assessment: skin, including mSWAT

9.3.6 Study Day 28 \pm 3 Days, Then Every 7 \pm 3 days: Delayed End of Cycle for Toxicity Resolution Only if Required**All Patients, All Study Stages:**

- Concomitant medication assessment
- ECOG performance status
- Vital signs and weight
- 12-lead ECG
- Clinical laboratory tests: hematology, serum electrolytes and chemistry (including albumin), coagulation parameters, and urinalysis
- AE and SAE monitoring

9.4 Cycles 2 – 6

Note: The end-of-cycle evaluations (Day 21 or thereafter) may also serve as the pre-infusion evaluations for the subsequent cycles; with the exception of vital signs, these do not need to be duplicated on successive days unless there is an abnormality or other clinically relevant reason for repeat evaluation.

9.4.1 Days 1 – 5 (Up to Day 10 if Infusion(s) Held): Pre-Infusion**All Patients, All Study Stages:**

- Inpatient admission (Day 1) or treatment at a suitable outpatient facility
- Vital signs and weight
- AE and SAE monitoring

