9.4.2 Days 1 – 5 (Up to Day 10 if Infusion(s) Held): Infusion

All Patients, All Study Stages:

- 12-lead ECG (Cycle 3 only, infusions 1 and 5) performed at 3 distinct time points (triplicates) within 5 minutes prior to each PK sample collection at 30 and 60 minutes post-infusion
- Collection of peripheral blood (plasma) for PK sampling (Cycle 3 only, infusions 1 and 5) collected immediately after end of infusion (time recorded), then 15, 30, 45, 60, 90, 120, 180 and 240 minutes after the completion of the infusion
- 15-minute IV infusion of SL-401 at required dose
- Vital signs: immediately after completion of infusion and 30, 60, and 240 minutes post-infusion
- Monitoring for at least 4 hours
- AE and SAE monitoring

9.4.3 Day 8 ±3 Days, or 3 ±3 Days after Completion of Infusions if Infusion(s) Held

All Patients, All Study Stages:

- Concomitant medication assessment
- Physical examination
- Vital signs and weight
- Clinical laboratory tests: hematology, serum electrolytes and chemistry (including albumin), coagulation parameters, and urinalysis
- AE and SAE monitoring

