9.4.4 Day 15 ±3 Days

All Patients, All Study Stages:

- Concomitant medication assessment
- Physical examination
- Vital signs and weight
- Clinical laboratory tests: hematology, serum electrolytes and chemistry (including albumin), coagulation parameters, and urinalysis
- AE and SAE monitoring

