- (n) Plasma samples (6 mL each) will be collected immediately prior to the start of the infusion of SL-401, immediately after end of infusion (time recorded), then 15, 30, 45, 60, 90, 120, 180, and 240 minutes after the start of the infusion during infusions 1 (i.e., Day 1) and 5 (i.e., Day 5) of Cycle 3 (see footnote (b) and [Table 9](#)).
- (o) Blood samples (10 mL) will be collected for the detection of SL-401 reactive antibodies according on Day 1 (pre-infusion), Day 15, and Day 21 (if patient is to receive additional cycles, can be Day 1, pre-infusion for next cycle). If infusions are held, please collect a sample within 3 \pm 3 days the last SL-401 infusion(s) of the cycle.
- (p) After the follow-up visit, patients will then be followed every 90 days for survival status. The survival follow-up may be by telephone contact. If the patient is in CR/PR at the time of discontinuation, disease assessments should continue to be performed as described in [Section 8.11](#) on an every 6-week basis (± 1 week) through 6 months post-C1D1 and then on an every 90-day basis or until, in the judgment of the Investigator, there is evidence of relapsed or progressive disease.

Table 7: Study Events Schedule for Cycles 1 & 2 (Study Day -14 to Study Day 21): BPDCN Patients in Stages 2-4

Tests and Observations	Study Day -14 to -4	Study Day -1 to 0	Cycles 1 & 2				
			Cycle Days 1-5 (Up to Study Day 10 if Infusion(s) Held) SL-401 Treatment		Study Day 8±3 ^(q) and 15±3	Cycle Day 21±7	Cycle Day 28±7, Then Every 7±3 days
	Screening	Pre-treatment	Pre-Infusion	Infusion		End of Cycle	Delayed End of Cycle for Toxicity Resolution Only if Required
Informed consent form	X						
Inclusion/exclusion criteria	X						
Medical history including prior therapy, concomitant medications	X						
Concomitant Medications		X			X	X	X
ECOG performance status	X					X	X
Physical examination	X	X			X	X	
Pregnancy test ^(a)	X						
Vital signs and weight ^(b)	X	X	X	X	X	X	X
12-lead ECG ^(c)	X	X	X	X (Infusions 1, 5)		X	X
ECHO or MUGA scan ^(d)	X						
Hematology ^(e)	X	X	X		X	X	X
Serum electrolytes ^(f)	X	X	X		X	X	X
Serum albumin ^(g)	X	X	X		X	X	X
Serum chemistry ^(h)	X	X	X		X	X	X
Coagulation parameters: PT/INR, aPTT	X		X		X	X	X
Urinalysis ⁽ⁱ⁾	X		X (Infusion 1)		X	X	X
Tumor response assessment: Bone marrow aspiration ± biopsy ^(j)	X					X	
Tumor response assessment: CT scan ^(k)	X					X (Cycle 2) ^(k)	
Tumor response assessment: Skin, including biopsies and/or photographs ^(l)	X					X	

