- (n) Following treatment with premedication, SL-401 will be administered as a 15-minute infusion for the first 5 consecutive days of a 21-day cycle. Individual SL-401 infusions may be delayed to allow for toxicity resolution; all infusions should be completed within 10 days and fewer than 5 infusions are permitted in settings of incipient CLS or hepatotoxicity. Patient must be monitored for 4 hours post infusion.
- (o) Plasma samples (6 mL each) will be collected immediately prior to the start of the infusion of SL-401, immediately after end of infusion (time recorded), then 15, 30, 45, 60, 90, 120, 180, and 240 minutes after completion of the infusion during infusions 1 (i.e., Study Day 1) and 5 (i.e., Study Day 5) of Cycles 1 & 3 (see [Table 9](#)).
- (p) Blood samples (10 mL) will be collected for the detection of SL-401 reactive antibodies on Day 1 (pre-infusion), Day 15, and Day 21 (if patient is to receive Cycle 2, can be Day 1, pre-infusion for Cycle 2). If infusions are held, please collect a sample within 3 \pm 3 days after completion of the last SL-401 infusion of the cycle.

Table 8: Study Events Schedule for Cycles 3-6 and Subsequent Cycles: Stages 2-4 (BPDCN Patients)

Tests and Observations	Cycle 3+					End of Treatment	Safety: Through 30 Days After Last Infusion	Survival: Every 90 Days After Last Infusion
	Days 1-5 (Up to Day 10 if Infusion(s) Held) SL-401 Treatment		Day 8±3 ^(q) and 15±3 ^(q)	Day 21±7	Day 28±7, Then Every 7±3 days			
	Pre-Infusion	Infusion		End of Cycle	Delayed End of Cycle for Toxicity Resolution Only if Required			
Medical history including prior therapy, concomitant medications								
Concomitant Medications			X	X	X			
ECOG performance status				X	X	X		
Physical examination				X		X		
Vital signs and weight ^(a)	X	X		X	X	X		
12-lead ECG ^(b)	X	X (Cycle 3, Infusions 1, 5)		X	X			
Hematology ^(c)	X		X	X	X			
Serum electrolytes ^(d)	X		X	X	X			
Serum albumin ^(e)	X		X	X	X			
Serum chemistry ^(f)	X		X	X	X			
Coagulation parameters: PT/INR, aPTT	X		X	X	X			
Urinalysis ^(g)	X (Infusion 1)		X	X	X			
Tumor response assessment: Bone marrow aspiration ± biopsy ^(h)				X ⁽ⁱ⁾				
Tumor response assessment: CT scan ^(j)				X				
Tumor response assessment: skin, including biopsies and/or photographs ^(j)				X				
Tumor response assessment: peripheral blood				X ^(k)				
Administration of premeds ^(l)	X							
SL-401 administration ^(m)		X						

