- (l) For patients with skin involvement. Baseline must be performed within 14 days prior to the first administration of tagraxofusp. Subsequent skin assessments will be performed 21 (\pm 7) days after the start of Cycles 1 and 2 and 21 (\pm 7) days after the start of every 2nd cycle thereafter (Cycles 4, 6, etc.) until there is evidence of relapsed or progressive disease. Quantification of skin disease burden via the mSWAT instrument is required at the time of each skin assessment.
- (m) In Cycle 1 and 3, and at end of treatment, Translational Assessment should be collected at Infusion 1 (Day 1), Infusion 5 (Day 5, 6, 7; if Infusion 5 does not occur by Day 8, please obtain this specimen on Day 8) and days 15, 21 (\pm 3 days, but must occur prior to start of subsequent treatment cycle). (n) Refer to protocol section 7.5.3 – Premedication and Administration
- (o) Following treatment with premedication, tagraxofusp will be administered as a 15-minute infusion for the first 5 consecutive days of a 21-day cycle. Individual tagraxofusp infusions may be delayed to allow for toxicity resolution; all infusions should be completed within 10 days and fewer than 5 infusions are permitted in settings of incipient CLS or hepatotoxicity. Patient must be monitored for 4 hours post infusion.
- (p) Plasma samples (6 mL each) will be collected immediately prior to the start of the infusion of tagraxofusp, immediately after end of infusion (time recorded), then 15, 30, 45, 60, 90, 120, 180, and 240 minutes after completion of the infusion during infusions 1 (ie, Study Day 1) and 5 (ie, Study Day 5) of Cycles 1 & 3 (see Table 10 in the protocol).
- (q) Blood samples (10 mL) will be collected for the detection of tagraxofusp reactive antibodies on Day 1 (pre-infusion), Day 15, and Day 21 (if patient is to receive Cycle 2, can be Day 1, pre-infusion for Cycle 2). If infusions are held, please collect a sample within 3 \pm 3 days after completion of the last tagraxofusp infusion of the cycle.

Table 7-4: Study Events Schedule for Cycles 3-6 and Subsequent Cycles: Stage 2 (BPDCN Patients)

Tests and Observations	Cycle 3+					Safety: Through 30 Days After Last Infusion	Survival: Every 90 Days After Last Infusion
	Days 1-5 (Up to Day 10 if Infusion(s) Held) Tagraxofusp Treatment		Day 8±3 _(q) and 15±3 _(q)	Day 21±7	Day 28±7, Then Every 7±3 days		
	Pre-Infusion	Infusion		End of Cycle	Delayed End of Cycle for Toxicity Resolution Only if Required		

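### Protocol Table 8 leaves out the Day 8 and Day 15 physical examination, vital signs and weight that Sections 9.4.3 and 9.4.4 require for BPDCN patients in Cycles 3-6

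*Protocol*

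**What the plan says.** Section 9.4 of the protocol covers Cycles 2-6. Two of its subsections, "Day 8 ±3 Days, or 3 ±3 Days after Completion of Infusions if Infusion(s) Held" (9.4.3) and "9.4.4 Day 15 ±3 Days", apply to all patients in all stages. Each lists a physical examination and vital signs with weight, along with laboratory tests, concomitant medication and adverse events.

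Section 7.5.4 begins its monitoring list with "Vital signs including blood pressure, heart rate, respiration rate, body temperature, and pulse oximetry" and schedules these on infusion days and on Days 8, 15 and 21. It sets no cycle limit, does not mention weight or examination, and sends the reader to the Section 9.8 tables for detail.

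The table in force for BPDCN patients in Stages 2-4 from Cycle 3 is "Table 8: Study Events Schedule for Cycles 3-6 and Subsequent Cycles: Stages 2-4 (BPDCN Patients". Its Day 8/15 column is marked for concomitant medication, all laboratory rows including albumin, urinalysis and adverse events. The physical-examination row is marked only at Day 21 and End of Treatment. The vital-signs row skips Day 8/15.

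Footnote (q), attached to that column, reads in part: "For Cycles 5 and beyond (Stages 2-4), the Day 8 and 15 concomitant medication and AE evaluations may be conducted via telephone". It goes on to allow local laboratories for patients who live far away.

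**The concern.** The text and the table give different instructions for the same patients, cycles and days, so a site cannot follow both.

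The missing items matter because capillary leak syndrome (CLS) was the principal dose-limiting toxicity (Section 3.8), and that section presents monitoring of vital signs, weight and albumin as part of its mitigation. Appendix E treats weight gain, edema and hypotension as CLS signs. In the earlier study, albumin was lowest about one week after the first infusion (Section 3.7.1). Table 8 keeps the Day 8 albumin but schedules no blood pressure, weight or edema check beside it.

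The SAP also uses these readings. Its CLS algorithm (Section 8.3) accepts systolic pressure below 90 mmHg and weight more than 5 kg from baseline as criteria, and needs two criteria that start within 7 days of each other.

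**Working it through.** The plan gives no figure to reproduce. The check is a comparison of schedules followed by simple gap arithmetic.

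**Is the blank real?** Neighbouring rows of Table 8 carry a mark in the Day 8/15 column, so the column was read correctly. The SAP's copy, "Table 7-4: Study Events Schedule for Cycles 3-6 and Subsequent Cycles: Stage 2 (BPDCN Patients", has the same two blanks. Protocol Table 6 (Stage 1 and AML, Cycle 2 onward) marks both rows at Days 8 and 15. So does "Table 7: Study Events Schedule for Cycles 1 & 2 (Study Day -14 to Study Day 21): BPDCN Patients in Stages 2-4". Table 8 is the exception.

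**Where do the schedules overlap?** The text runs from Cycle 2 to Cycle 6 and Table 8 starts at Cycle 3, so the direct conflict is Cycles 3-6. Cycle 2 falls under Table 7, which agrees with the text. After Cycle 6 only Section 7.5.4 could still require the vital signs.

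**Does footnote (q) explain it?** No. It starts at Cycle 5, so it cannot cover Cycles 3-4, and it names neither item.

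**Blood pressure and weight: longest scheduled gap after a Day 5 last infusion**

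| | Table 8 alone | Text |
|---|---|---|
| Nominal days | 21 - 5 = 16 | 8 - 5 = 3; 15 - 8 = 7; 21 - 15 = 6; maximum 7 |
| With visit windows | 14 - 5 = 9 to 28 - 5 = 23 | up to 28 - 12 = 16 |
| Infusions held to Day 10, nominal | 21 - 10 = 11 | 13 - 10 = 3; 15 - 13 = 2; 21 - 15 = 6; maximum 6 |

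The windows are Day 15 ±3 (earliest Day 12) and Day 21 ±7 (Days 14 to 28). The upper ends assume that the next cycle has not started before a late end-of-cycle visit.

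**Physical examination, nominal days.** The list under "9.4.1 Days 1 – 5 (Up to Day 10 if Infusion(s) Held): Pre-Infusion" has vital signs and weight but no examination, so infusion days do not help. With the previous end-of-cycle visit as day 0:
- Table 8: 21 - 0 = 21 days.
- Text: 8 - 0 = 8, 15 - 8 = 7, 21 - 15 = 6; maximum 8.
- A patient given k of Cycles 3-6 has k scheduled examinations under Table 8 and 3k under the text: 1 to 4 against 3 to 12, excluding End of Treatment.

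The windows can lengthen both maximum gaps, so 21 and 8 are not bounds.

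**Effect on the CLS algorithm, nominal days.** A low Day 8 albumin can still pair with a Day 5 reading (8 - 5 = 3 days), and a low Day 15 albumin with a Day 21 reading (21 - 15 = 6 days). What Table 8 drops is any scheduled reading from Day 6 to Day 20. A brief fall in pressure or gain in weight in that span would enter only through an unscheduled reading, an adverse-event term or a listed vasopressor.

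**The case against.** The strongest reply is that Table 8 is only a summary. Section 9 says so, and an empty cell does not clearly cancel requirements stated in 9.4.3, 9.4.4 and, for vital signs, 7.5.4. A site that reads the whole protocol would take the readings. This is a fair limit: the gaps above apply only to a site working from the table alone. It does not remove the conflict, because 7.5.4 itself refers back to the tables, and weight and examination rest on 9.4.3 and 9.4.4 only.

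The blanks may also be deliberate. Every row kept at Days 8 and 15 can be done by telephone or at a local laboratory, while the two dropped rows need attendance. That is plausible, but no text states it, and the remote option does not reach Cycles 3-4.

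Three stronger readings are tempting and are not supported:
- *The 16-against-7 contrast is a bound.* It holds on nominal days only. A site following the text within its windows could also go 16 days.
- *CLS goes undetected in later cycles.* The albumin timing comes from a single-cycle study, Cycles 1-2 are fully monitored under Table 7, and the documents give no CLS timing for Cycle 3 onward.
- *Readings were missed, or safety results are biased.* The documents do not say which schedule sites followed.

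**Conclusion.** The inconsistency holds for BPDCN patients in Stages 2-4, Cycles 3-6, and is minor. Read alone, Table 8 leaves a nominal 16 days without scheduled blood pressure or weight, against a nominal maximum of 7 under the text. With the windows the ranges overlap (9 to 23 days against up to 16). It also leaves no examination between end-of-cycle visits.

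The consequences are limited. Albumin, chemistry, adverse-event and concomitant-medication checks stay at Days 8 and 15. No dosing rule uses the missing readings: the weight trigger in Table 4 and Appendix E compares successive treatment days. Efficacy, power and type I error are unaffected. Patient listings (SAP 4.4.4) will show which readings exist. The clinical effect cannot be sized. With enrollment ended in January 2019 and a data cutoff of 13 March 2020 (SAP 1.1 and 3.13.4), the practical gain is mostly in how existing data are presented.

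**What to change.** Mark physical examination and vital signs with weight at Day 8/15 in Table 8 for Cycles 3-6, to match 9.4.3, 9.4.4 and, for vital signs, 7.5.4. State in footnote (q) whether the remote option from Cycle 5 covers these items. Say whether the Day 8/15 vital signs in 7.5.4 apply after Cycle 6. If the lighter schedule was intended, amend 9.4.3, 9.4.4 and 7.5.4 instead.

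For data already collected, add one table of Day 8/15 blood pressure and weight availability by cycle, next to the CLS summaries in SAP 4.4.2.1. SAP 4.4.4 limits vital-sign tables to visits where at least 10% of the analysis population was measured, so sparse Day 8/15 visits might otherwise appear only in listings.

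The cost is two table rows, a footnote line and one output. The first option adds no procedure beyond what the text requires, but either option is a protocol amendment and needs the approvals in Section 14.5. If no patient is still on treatment, only the availability table is worth doing.
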